2.11 If applicable, are health service research issues to be addressed?

This pilot is aimed at establishing effect sizes, so we will include health economics in a future larger RCT.

2.12 What is the planned recruitment rate? How will the recruitment be organized? Over what time period will recruitment take place? What evidence is there that the planned rate is achievable?

We will use the combination of methods we often use to recruit women with sexual difficulties.^{9,17,43} These include: (i) online postings (e.g., social media, Craigslist, women-specific groups); (ii) sending letters to ~100 BC primary care providers to request they inform patients about the study; (iii) paid advertisements in newspapers; and (iv) posted recruitment ads in the community on public boards (e.g., gyms, community centres, coffee shops, etc.). We have made a commitment to oversampling for trans women, given evidence that they face high levels of sexual dysfunction and tend to be omitted in research.¹⁰¹ We tailor our methods to ensure a consistent rate of recruitment, and will check sampling every 3 months to ensure we are accessing potential populations of trans women. We are not including trans men or non-binary individuals because the online materials refer to "women" throughout.

2.13–2.14 Are there likely to be any problems with compliance? On what evidence is this based? What is the likely rate of loss to follow up? On what evidence is this based?

Adhering to navigator schedule: If participants exhibit a consistent difficulty in scheduling Zoom sessions and/or has difficulty accessing a webcam of high enough quality to allow for effective interaction, we will allow participant-navigator meetings to take place by phone.

Attrition: Strategies to minimize attrition include: engaging intervention materials; trained, dedicated navigators; explicit discussion of required time commitment; and stepped compensation schedule. The study coordinator will send participants and navigators reminder e-mails about all Zoom sessions (on the day before) and reminders to complete online measures. Two more e-mails will be sent if there is no response.¹⁰² If participants still do not engage in a session or complete scheduled measures, they will be phoned by the study coordinator.¹⁰³

Compliance: We will compare compliance rates to previous research. One systematic review¹⁰⁴ found a typical adherence rate of ~50% in internet interventions for anxiety and depression. Given the aspects of our study meant to maximize adherence (e.g., engaging web content, individualized support, reminder e-mails), we expect our rates to be at least this high. Rates of treatment completion will be compared to other trials of online treatments for FSD and to web-based interventions more broadly. Systematic reviews of drop-out rates from online therapy with minimal support suggest typical attrition of ~30%.¹⁰⁵ Reported rates in online treatment of FSD are comparable (35%)⁷³ or higher (54%).⁸³ We will compare our attrition rate to 30% using a one-sided binomial test, to determine if it is significantly higher in our study.

Alternate Treatment: We will propose to participants who report no significant improvement after a year try the alternate treatment. We will also ask participants who drop out if they are willing to try the alternate treatment (if time is not a factor). We will not be collecting data in the alternate treatment as this is not a true test of their participation given that they will have already received one treatment.

2.15 How many centres will be involved?

Though the team of investigators come from 4 different institutions, all study activities will take place in the NPA's laboratory at UBC.

2.16–2.18 What is the proposed type of analyses? What is the proposed frequency of analyses?

Statistical analysis: Effect of treatment will be determined by analyzing baseline (pre) to post-treatment changes after CBT-O and MBT-O on sexual distress (FSDS-R) and sexual desire (SIDI) scores. Sustainability of treatment effects will be evaluated by adding the follow-up measurement point to the model. Both analyses will be conducted using a multilevel mixed effect model analysis with one within-subject factor of time (treatment) based on 2 or 3 measurement points (baseline and post-treatment in the first analysis; plus 6-month follow-up for the second analysis) and one between-subject factor (CBT-O vs MBT-O) as well as their interaction. Interactions will test for differences in the amount of change due to treatment between arms. We will calculate effect sizes and confidence intervals (CI) and use descriptive statistics for measures of treatment satisfaction and compliance. These values will be compared between treatment arms. Treatment length will vary from 8 to 12 wks, so individual length of treatment will be added as a control variable in all initial models. Notable differences will guide changes that may increase satisfaction/compliance before we conduct a larger RCT following completion of the current pilot study.

Missing data: Mixed-effects modelling allows for missing data and uses all available data for estimating model parameters. Incomplete outcome data can restrict the sample size available for tests of interactions. We will impute missing outcome data using multiple imputation techniques. We will run a sensitivity analysis to compare analysis that uses multiply-imputed data to analysis that includes missing data.

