1.2 What is/are the principal research question(s) to be addressed?

The primary aims are to:

1. Determine the efficacy of two online (O) versions of empirically-supported psychotherapies for treating FSD: *Cognitive-Behavioural Therapy (CBT-O)* and *Mindfulness-Based Therapy (MBT-O)* compared to a wait list. Primary endpoints are changes in sex-related distress and sexual desire from pre- to post-treatment and persistence of improvement at 6-month follow-up.
2. Compare CBT-O with MBT-O for treating FSD, measuring pre- to post-treatment change in sex-related distress and sexual desire and sustainment of improvement at 6-month follow-up.
3. Evaluate participant satisfaction and compliance using these online programs with weekly individualized support from a non-expert navigator.

We ([name], [name], [name]) are experts in CBT and/or MBT for face-to-face and web-based treatment of sexual difficulties.⁹⁻¹⁷ We have worked with [name], a professional graphic and digital designer, to develop **eSense**: an online platform to deliver CBT and MBT treatments adapted for web-based, self-directed therapy. We believe that eSense is efficacious, has the potential to improve accessibility and affordability of evidence-based treatment, and has long-term potential to be commercialized. I ([name]) am lead creator and evaluator of the most widely-validated MBT intervention for FSD,¹⁸ which can be readily adapted for online use. To our knowledge, there is no equivalent CBT intervention for FSD that is comprehensive and available. Therefore, much of our work to date has focused on creation and testing of the CBT “arm” of eSense.

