2. THE PROPOSED TRIAL

2.1 What is the proposed trial design?

This is a 3-arm RCT comparing CBT-O and MBT-O to a wait-list control (Study timeline, **Appendix**).

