2.3 What are the proposed practical arrangements for allocating participants to trial groups?

Randomization: Participants will be randomized to one of 3 arms in a 1:1:1 sequence (CBT-O: MBT-O: wait-list control) using the Blockrand package in R, with random block sizes. Those in the wait-list group will complete two online questionnaire/assessment batteries before being randomized to one of the active treatment groups. As indicated in the Figure (next page), the n=30 women randomized to wait-list will be enrolled in a treatment arm after the wait-list period is complete. No stratification will be used in this pilot study.

Waitlist control: Face-to-face FSD intervention studies consistently find no passage-of-time-only changes in participants assigned to waitlist control groups^{11,58}. As such, to maximize the opportunity to estimate treatment effects while minimizing costs of this pilot study, we propose a **modified waitlist control group**. At study onset, participants will be assigned randomly to the waitlist group; at the end of the waiting period, they will be randomized into 1 of the 2 treatment groups. They will receive 2 assessments: at waiting period start and after randomization to treatment (Fig 1, next page). Pre- and post-waiting period assessments will be compared to check for a passage-of-time effects. Starting at post-waiting period assessment, their data will be combined with the rest of the participants for treatment evaluation analyses.

What are the proposed methods for protecting against sources of bias?

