Assessment points: CONSORT²⁸ guidelines will be followed in terms of tracking number of participants recruited, randomized, and retained through assessment and treatment. For CBT-O and MBT-O groups, there are 3 assessment points (baseline; post-treatment (within 2wks of completing the 8-module program); and 6-month follow-up). For the wait-list group, there are 2 pre-treatment assessments at waiting period start and after randomization to treatment (4 assessment points; same online questionnaires). No treatment will be given to wait-list participants during this waiting period. However, after the second online questionnaires are complete, they will be randomized to either the CBT-O or MBT-O arm of eSense. All participants will also be sent a mid-treatment link to an online question that asks them to write freely about their reactions to the treatment to date. This is included to examine quality assurance of the intervention. To minimize attrition, honoraria will be linked to completion of each assessment point: \$30 for (each) baseline assessment, and \$40 at post-treatment and 6-month follow-up assessment points.

Protocol: All participation will be remote, requiring no in-person meetings. Prospective participants will contact the study coordinator at UBC via e-mail, then set up a phone screen for inclusion/exclusion criteria (Fig 1). Consent forms will be sent to prospective participants prior to the scheduled phone screen by the study coordinator. Women will be informed of the length of the intervention (8 modules; 8-12 wks), expectations for homework (1-2 hours/week), and the use of treatment navigators. After meeting the screening criteria, the study coordinator will send prospective participants a personalized link to a Qualtrics questionnaire battery. The first page of the questionnaires will be the e-consent form. Participants must read and electronically sign the consent form before they move on to the baseline questionnaires. The e-consent form will indicate that any questions/issues they raise in interactions with study staff that are worrisome (e.g., suicidal ideation) will automatically prompt the coordinator to contact them. Women who choose not to participate will be provided with other resources (websites, directories of sex therapists, books).

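### No planned analysis compares CBT-O or MBT-O with the wait-list, so Aim 1 would rest on uncontrolled pre-post change

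*Combined protocol and SAP*

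**What the plan says.** Section 1.2 sets Aim 1 as the efficacy of CBT-O and MBT-O "compared to a wait list. Primary endpoints are changes in sex-related distress and sexual desire from pre- to post-treatment". Section 2.1 agrees: "This is a 3-arm RCT comparing CBT-O and MBT-O to a wait-list control". Section 2.3 randomises 1:1:1.

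The statistical analysis (sections 2.16–2.18) defines the effect differently: "Effect of treatment will be determined by analyzing baseline (pre) to post-treatment changes after CBT-O and MBT-O". The mixed model has a time factor, a two-level program factor (CBT-O, MBT-O) and their interaction. Length of treatment is a covariate in all initial models. Section 2.10 likewise bases power on two treatment groups.

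Section 2.3 calls the control a modified wait-list and gives its reason: "Face-to-face FSD intervention studies consistently find no passage-of-time-only changes in participants assigned to waitlist control groups". The waiting-period scores have one stated use: "Pre- and post-waiting period assessments will be compared to check for a passage-of-time effects". After that, "Starting at post-waiting period assessment, their data will be combined with the rest of the participants for treatment evaluation analyses".

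**The concern.** The aim and the design promise a between-group comparison that the model cannot produce, because the wait-list is not a level of any factor in it. The interaction answers Aim 2, CBT-O against MBT-O. That leaves the time main effect to carry Aim 1. This is within-person change, which mixes any program effect with regression to the mean (women must meet diagnostic criteria at screening), repeated measurement and natural improvement.

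The check in section 2.3 does not fill the gap. It is a test within one group, and no rule links its result to the efficacy conclusion or to the pooling. The expectation of no drift comes from face-to-face studies, whereas this trial is online. The first randomisation is therefore never used to estimate efficacy. Section 1.4 would carry effect sizes that include any drift into planning the larger trial.

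**Working it through.** **1. The plan's own numbers.** Section 2.10 needs 75 participants for 90% power, with two treatment groups and alpha 0.05. A two-sample t-test at d=0.80, two-sided, needs 68 in total, so 75 is not reproduced exactly. The software procedure, the sidedness and the correlation between outcomes are not given, so this does not show 75 to be wrong. The recruitment figure does follow from 90 completers: 90/0.7 = 128.6, or 129, and 43 × 0.7 = 30.1 per arm. Nothing in section 2.10 sizes a comparison with the wait-list.

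**2. Which analysis serves which aim.**

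| Question | Analysis given | Uses wait-list as comparator? |
|---|---|---|
| Aim 1, each program vs wait-list | Time effect in treated women | No |
| Aim 2, CBT-O vs MBT-O | Time × program interaction | No |
| Change over the wait | Pre/post within wait-list group | No |

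**3. Drift in scale points.** Section 2.19 gives paired t values and means for face-to-face MBT. SD of change = mean change × √n / t.
- FSDS-R: 9.4 × √58 / 6.43 = 11.13.
- SIDI: 11.0 × √59 / 8.13 = 10.39.

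Drift of 0.1 to 0.4 SD of change is then about 1.1 to 4.5 FSDS-R points or 1.0 to 4.2 SIDI points. The drift values are assumptions; the documents give none.

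**4. What the planned tests do if the programs have no effect.** These are exact noncentral-t probabilities for a paired test, two-sided 0.05, with noncentrality drift × √n. The pooled n is 3 × 30 = 90. The wait-list n is 30 (section 2.3), or 43 if all those recruited to the arm (section 2.10) are assessed. The joint rows give a significant pooled test together with a non-significant check, treated as independent; for example, at drift 0.3, 0.804 × (1 − 0.355) = 0.52.

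| Drift (SD of change) | 0.1 | 0.2 | 0.3 | 0.4 |
|---|---|---|---|---|
| Pooled pre-post significant, n=90 | 16% | 47% | 80% | 96% |
| One program significant, n=45 | 10% | 26% | 50% | 75% |
| Check detects drift, n=30 | 8% | 19% | 36% | 56% |
| Check detects drift, n=43 | 10% | 25% | 49% | 73% |
| Joint, check n=30 | 14% | 38% | 52% | 42% |
| Joint, check n=43 | 14% | 35% | 41% | 26% |

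The two tests share the post-wait score. Simulation allowing for this (20,000 replicates, 60 immediate and 30 post-wait women) gives joint figures of 14/41/55/43% at n=30 and 15/38/44/27% at n=43. If wait-list women use up their drift during the wait, pooled significance falls to 9/24/46/70% and the joint figure at n=30 to 9/21/34/34%. At zero drift the pooled test is valid at 5%.

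The check reaches 80% power only for a change of 0.53 SD of change at n=30, or 0.44 at n=43.

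**5. The randomised contrast.** With equal drift in both arms, its false-positive rate stays at about 5% at every drift value. If the wait carried drift of 0.2 and the active arm 0.4, the remaining difference of 0.2 would be significant about 12% of the time at 30 per arm.

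**6. Its power.** Two-sample t, 30 per arm, two-sided 0.05. The first three effect sizes are those cited in section 1.3. Baseline adjustment at an assumed correlation of 0.5 multiplies the residual SD by √(1 − 0.5²) = 0.866.

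| d | 0.47 | 0.52 | 0.58 | 0.80 |
|---|---|---|---|---|
| Unadjusted | 43% | 51% | 60% | 86% |
| Baseline-adjusted | 54% | 63% | 72% | 94% |

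Unadjusted, 80% power needs d=0.74. The 95% CI half-width at d=0.5 is about 0.51 SD.

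**The case against.** The strongest reply is that this is a disclosed trade-off. Section 2.3 names the modified wait-list and says it is meant to maximise estimation of treatment effects at low cost. Section 2.11 says the pilot aims at effect sizes. Rewording Aim 1 and section 2.1 as uncontrolled pilot estimates would also remove the contradiction. That is true, but it would discard a randomised comparison whose data are already to be collected.

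The false-positive figures are a worst case: they assume no program effect and a drift that the documents do not report. The evidence cited in sections 1.3 and 2.19 points to real effects. This stands as a limit on the size of the problem. The more direct harm for the larger trial is bias in the effect size, equal to whatever drift there is. The joint figures also read the check as pass or fail, which section 2.3 does not say. The n=43 rows may suit it better than n=30, since fewer women will have been lost by the end of the wait than by the end of treatment.

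The 5% rate for the randomised contrast also has conditions: a wait comparable in length with treatment, and no differential loss. That stands too, and the fix has to deal with it. None of these points supplies the missing comparison.

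**Conclusion.** The concern holds and must be fixed. No section specifies a contrast of either program with the wait-list, so the first primary aim would go without an estimate. That conclusion comes from the text and depends on no assumed number.

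The size of the risk does depend on assumptions. With no program effect and drift of 0.1 to 0.4 SD of change, the pooled test is significant in 16% to 96% of trials. A wait-list check of 30 women often fails to flag the drift. With no drift there is no inflation, but the promised comparison is still absent.

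**What to change.** Make the primary Aim 1 analysis the randomised comparison over the first period:

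- Include all women by original allocation, with a three-level arm factor. Compare FSDS-R and SIDI at post-treatment (active arms) with end of wait (wait-list), adjusted for baseline. Use the multiple imputation and sensitivity analysis already planned.
- Report CBT-O vs wait-list and MBT-O vs wait-list with 95% CIs, and let the estimates lead. State how the four comparisons (two programs × two outcomes) are handled.
- Leave treatment length out of this model; it is undefined for untreated women.
- State the wait length beside the analysis and that it is comparable with the 8–12 week treatment window. The length is not in the text available, and a figure is not shown.
- Reconcile the timing of the second wait-list assessment. Section 2.3 has "They will receive 2 assessments: at waiting period start and after randomization to treatment"; sections 2.6–2.7 have "after the second online questionnaires are complete, they will be randomized to either the CBT-O or MBT-O arm of eSense". It is a clean end-of-wait outcome only if taken before the new allocation is known.
- Keep the pooled data for Aim 2, with an indicator for immediate or post-wait entry. Describe the 6-month result as uncontrolled maintenance.

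This takes analysis wording and one added model, with no new data or participants. The real cost is precision, and the estimates may be smaller than the pre-post ones. Power at the cited effects is modest, as shown above, and a Bonferroni correction over four tests (alpha 0.0125) would lower unadjusted power at d=0.80 from 86% to 70%.

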2.10 What is the proposed sample size; justification for assumptions underlying power calculations?

Based on our findings,¹⁷ we expect large effect sizes for the main outcomes ($d=.8$ for FSFI and $d=1.05$ for FSDS-R) in the MBT-O arm. According to power analysis based on these two measures and two treatment

groups, 75 participants are needed to give us 90% power to discover a large size effect of our treatment at alpha level of .05 (PASS, 2019 Power Analysis and Sample Size Software (2019). NCSS, LLC. Kaysville, Utah, USA, [ncss.com/software/pass.](http://ncss.com/software/pass/)). Based on [name]'s work, we expect ~30% attrition so we will recruit 129 women (n=43 per arm) (control later randomized to treatment). After attrition, we expect to have n=30 in each arm.

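### The analysis names one time effect shared by CBT-O and MBT-O and no contrast for each program, so the stated tests do not match Aim 1, which asks about each program

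*Combined protocol and SAP*

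**What the plan says.** Section 1.2, Aim 1, is to "Determine the efficacy of two online (O) versions of empirically-supported psychotherapies for treating FSD", naming CBT-O and MBT-O, each compared with a wait list. The primary endpoints are sexual distress and sexual desire, before to after treatment and at 6 months. Comparing the two programs with each other is Aim 2.

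Section 2.16–2.18 (Statistical analysis) says the effect of treatment comes from pre-to-post changes after both programs on FSDS-R and SIDI. The mixed model has "one within-subject factor of time (treatment) based on 2 or 3 measurement points", a two-level program factor and their interaction. The interaction has one stated job: "Interactions will test for differences in the amount of change due to treatment between arms". The section does not state the factor coding, a contrast for each program, or any rule linking the interaction to an efficacy claim. Effect sizes and confidence intervals are promised, and values are to be compared between arms, but in a sentence that also covers satisfaction and compliance and sets no rule for either program on the primary outcomes.

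Section 2.3 allocates 1:1:1 to CBT-O, MBT-O and wait list. Wait-list women are later randomized to a program, and their data then join the treatment analyses. Section 2.10 adds: "After attrition, we expect to have n=30 in each arm".

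**The concern.** Aim 1 contains two null hypotheses, one per program. The model's named tests address neither as a pair. With sum-to-zero coding, the time effect asks whether the mean of the two changes is zero. With reference coding, it asks about the reference program and is silent on the other. The interaction asks whether the programs differ; a non-significant result does not show that both work.

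One program working better than the other is plausible on the protocol's own account: section 1.3 says head-to-head comparisons of CBT and MBT are sometimes equal and sometimes favor one or the other. In that case a significant time effect could be written up as efficacy of both programs, and a pooled change would be a poor effect size for planning the larger RCT. This is separate from the question of how the wait list is used: averaging over programs misleads even if wait-list women do not change at all.

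**Working it through.** **Inputs from the plan**
- Two-sided alpha .05. Section 2.10 gives .05 without sidedness; two-sided is assumed.
- Women per program: 30 (section 2.10, after attrition), or 45 once 30 wait-list women are split evenly (30 + 15).
- Effect of 0.85: section 2.19 gives t(57) = 6.43 for distress in the face-to-face MBT trial, so 6.43/√58 = 0.84; the section reports 0.85.
- Effect of 0.5: an assumed moderate value, used to show the range.

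**The plan's own figures.** Recruitment reproduces: 90/0.70 = 128.6, so 129, and 43 × 0.70 = 30.1 per arm. The statement that "75 participants are needed to give us 90% power to discover a large size effect of our treatment at alpha level of .05" could not be reproduced by standard two-sample, paired, ANOVA or two-outcome calculations. The procedure and correlations are not given, so it is not called wrong, and nothing below depends on it.

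**Set-up.** Balanced design, n women per program, standard deviation of change = 1 in both programs, true changes dA and dB, 2n − 2 degrees of freedom.
- Time effect (average change): noncentrality = ((dA + dB)/2) × √(2n)
- Interaction (difference in change): noncentrality = (dA − dB) × √(n/2)
- One program's own change: noncentrality = dA × √n

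**One program inert (dB = 0).** The first two noncentralities are then equal, since (d/2)√(2n) = d√(n/2). Time and interaction therefore have the same power.

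| n per program | d | Noncentrality | Time significant | Time significant, interaction not | Inert program's own contrast significant |
|---|---|---|---|---|---|
| 30 | 0.5 | 0.25 × √60 = 1.94 | 47.8% | 24.5% | 5% |
| 45 | 0.5 | 0.25 × √90 = 2.37 | 65.0% | 22.5% | 5% |
| 30 | 0.85 | 0.425 × √60 = 3.29 | 89.9% | 9.0% | 5% |
| 45 | 0.85 | 0.425 × √90 = 4.03 | 97.9% | 2.1% | 5% |

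The time column is from the noncentral t distribution; the last two columns are from 200,000 simulated trials per setting. As a check, the two estimates are independent in a balanced design, so the fifth column should be close to p(1 − p): 0.478 × 0.522 = 0.250 and 0.899 × 0.101 = 0.091.

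**Power of the alternatives at d = 0.5**
- Both programs work, pooled time test: noncentrality 0.5 × √60 = 3.87 gives 97%; 0.5 × √90 = 4.74 gives over 99%.
- One program's own change: 0.5 × √30 = 2.74 gives 77%; 0.5 × √45 = 3.35 gives 91%.
- One program against wait list, 30 women each, if the wait list does not change: 0.5 × √(30/2) = 1.94 gives 48%. At 0.85 the same contrast gives 90%.

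**The case against.** The strongest reply is that the plan never says efficacy will be declared from the time main effect. It speaks of changes after both named programs, and the model, with its interaction, contains each program's change. Labelling a factor is not a decision rule. This stands: the plan leaves the program-specific contrast unstated; it does not rule it out.

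Second, the interaction is tested. At large effects it would usually expose an inert program, so a reader who took 90–98% as the plan's false-claim rate would be wrong; at d = 0.85 the unflagged share is 2–9%. This also stands, with two limits: at d = 0.5 the share is 22–25%, and the plan does not make an efficacy claim depend on the interaction.

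Third, a reader might infer that MBT-O is the doubtful program because its support is only face-to-face. Section 1.3 does not allow that: it mentions preliminary data from a web-based study covering both CBT-O and MBT-O, although without separate results.

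Fourth, nothing says a significant time effect would carry both programs into the larger RCT. The stated purposes include estimating effect sizes and comparing the treatments. That is correct, but those effect sizes also need to be program-specific.

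Finally, Aim 1 defines efficacy against a wait list, so an uncontrolled pre-to-post contrast cannot be its criterion. This stands and shapes the fix.

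**Conclusion.** The concern holds as a mismatch between aim and analysis: Aim 1 asks about each program, while the stated tests address an average (or a single reference program) and a difference. It should be corrected, but it is not evidence that the plan intends a pooled efficacy claim.

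If one program is inert, the shared time test is significant in about 48–65% of trials at d = 0.5 and 90–98% at d = 0.85. The more relevant figure, significant time with no interaction to flag the problem, is about 22–25% and 2–9%. These figures assume factorial coding, exactly zero change in the inert program, equal standard deviations of change, a balanced split, and 30 to 45 women per program. The 5% rate for the inert program's own contrast also rests on zero change without effective treatment, which is why the wait-list comparison matters.

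**What to change.** In section 2.16–2.18:
1. Pre-specify, from the same fitted model, the change from baseline to post-treatment and to 6 months for CBT-O and for MBT-O separately, with estimates and 95% confidence intervals for FSDS-R and SIDI.
2. State that neither the time main effect nor a non-significant interaction supports a claim for an individual program.
3. Base any Aim 1 efficacy claim on each program's change compared with wait-list change over the waiting period. Say how the model handles wait-list women who later contribute to a program. Treat the uncontrolled within-program change as descriptive and as the effect-size estimate for the larger RCT.
4. State how multiplicity is handled across two programs and two primary outcomes (2 × 2 = 4 comparisons).

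The cost is a few sentences and no new data. The price is power. At d = 0.5 a within-program contrast has about 77% (30 women) or 91% (45 women), against 97% and over 99% pooled when both programs work. A comparison of 30 women with 30 on the wait list has about 48% at d = 0.5 and 90% at d = 0.85, before any multiplicity adjustment. For a pilot this favors reporting intervals over significance alone.
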